## Abbreviations

AI/AN	American Indian/Alaska Native
AOD	Alcohol and other drug
EA	Emerging adults
EAB	Elder Advisory Board
FG	Focus group
HEAL	Helping End Addiction Long Term
MICUNAY	Motivational Interviewing and Culture for Urban Native American Youth
OUD	Opioid use disorders
TACUNA	Traditions and Connections for Urban Native Americans
WC	Wellness Circle

# Study Protocol

*A clinical study or research protocol guides the study and associated data collection and analysis in a productive and standardized manner and is carefully designed to safeguard the participants' health and answer specific research questions. The protocol should describe the following aspects of the study.*

## 1. What the study will do

This study responds to Request for Application-DA-19-035, HEAL (Helping End Addiction Long Term) initiative: Preventing OUD in Older Adolescents and Young Adults (ages 16-30) by developing and implementing a culturally centered intervention to address opioid use among urban American Indian/Alaska Native (AI/AN) emerging adults. The primary goal of this behavioral study is to compare AI/AN emerging adults who receive TACUNA (Traditions and Connections for Urban Native Americans) plus a Wellness Circle (WC) to those AI/AN emerging adults who receive an opioid education workshop on outcomes (e.g., opioid misuse and alcohol and other drug use) over a period of 12 months.

- TACUNA will be a virtual motivational interviewing group intervention that incorporates traditional practices and discussion of how to cultivate healthy social networks and cultural worlds. The Wellness Circle will be for emerging adults and people in their social network and will focus on how social networks and cultural connectedness influence healthy behaviors.
- Opioid education (control) will focus on discussion of opioid misuse within the AI/AN urban community and ways to reduce use in a culturally appropriate manner.

## 2. How it will be done

### Phase 1/UG3

**Aim 1.** We will conduct focus groups (FGs) with emerging adults (EAs), parents of EAs, AI/AN providers, and our Elder Advisory Board (EAB) in urban communities throughout California to understand how to a) best identify, reach and engage AI/AN EAs to access programming addressing opioid use, b) adapt and enhance our existing culturally sensitive prevention intervention program, Motivational Interviewing and Culture for Urban Native American Youth (MICUNAY), for AI/AN EAs to address social network factors that amplify (or reduce) opioid and AOD use risk, and c) conduct a pilot test to ensure feasibility and acceptability of the TACUNA program.

### Phase 2/UH3

Note: Due to the COVID-19 pandemic and restrictions on social gatherings, this study pivoted from in-person group implementation to virtual group implementation. This allowed us to expand participation beyond our original urban sites in California as we were no longer limited by facilitating in-person groups.

In Native American research, it is typical that intervention and control groups receive some degree of an intervention. We will enroll 370 participants at baseline across the United States who we determine represent the broader population of 18-25 year old urban AI/AN emerging adults. In a randomized controlled trial—an unmasked, 2-arm parallel intervention model—participants either will be assigned to TACUNA (n = 185), which comprises three virtual workshops utilizing motivational interviewing, social network visualization, and integrating traditional practices and a Wellness Circle (WC), or to one virtual culturally sensitive opioid education workshop (n = 185). WCs will be culturally focused, and feature Native foods and entertainment (e.g., Native lectures, storytellers, cooking demonstrations, and sage ceremony).

**Aim 2.** We will compare AI/AN EAs who receive TACUNA+WC to AI/AN EAs who receive opioid education. We will compare outcomes at 3, 6, and 12-months to determine (a) whether changes occur in initiation and escalation of opioid use and alcohol and other drug use, such as cannabis, and related consequences; time spent around peers who use opioids and AOD, and perceived prevalence of peer use, (b) whether clinically significant changes occur in physical, social, emotional, and functional well-being, as well as spirituality and cultural connectedness, and (c) if reductions occur, estimate effect sizes.

**Aim 3.** We will explore potential mechanisms of change for decreases in opioid and AOD use outcomes through mediation analyses, including changes in social networks and cultural connectedness.

**Aim 4.** We will develop and test strategies to facilitate sustainability of TACUNA within these communities through key informant interviews upon conclusion of the randomized controlled trial.

**Aim 5.** We will conduct an economic evaluation to quantify programmatic costs and cost-effectiveness of the multi-tiered intervention approach, relative to opioid education.

### **3. Why it is being done**

This study's primary purpose is prevention. To date, there are no evidence-based prevention programs addressing opioid use among urban AI/AN emerging adults that integrate culturally appropriate strategies with evidence-based treatment. TACUNA builds on our prior work with AI/AN communities to develop and evaluate culturally appropriate programming to address opioid, alcohol, and cannabis use among urban AI/AN emerging adults.

Data from 2015 show that AI/AN people have the highest rates of diagnosis for opioid use disorders (OUD) and deaths from drug overdose. Unique risk factors may predispose urban AI/AN young adults to use opioids, alcohol or other drugs. For example, experiences of acculturative stress directly and indirectly associated with historical trauma experienced by AI/AN people throughout U.S. history result in poor health outcomes.

Programming that incorporates traditional practices, promotes community involvement, and encourages healthy notions of AI/AN identity may increase well-being and healthy behaviors by addressing sources of stress linked to cultural identity, stigma, and community connections. However, few evidence-based programs that integrate these cultural elements have been developed, implemented, and evaluated with urban AI/AN people using a strong research design. The TACUNA study substantially extends work with AI/AN emerging adults by adapting and testing an integrated culturally appropriate MI and social network intervention to address opioid and other AOD misuse at both the individual and community level.

### **4. How many people will be in the study**

We will enroll 370 participants at baseline who we determine represent the broader population of urban AI/AN emerging adults. This sample size was determined in a priori power analyses to be sufficient to detect small to moderate intervention effect sizes for all primary and secondary outcomes.

### **5. Who is eligible to take part in it**

Eligibility criteria include: 1) ages 18 to 25; 2) living in an urban area in any state in the United States (not on a rancheria or a reservation); 3) self-identification as AI/AN; 4) no opioid use disorder; and 5) English speaking.

## 6. What study therapy or other interventions will be given

None.

## 7. What tests will be done and how often

No tests will be done. Survey data will be collected at baseline, 3 months, 6 months and 12 months.

## 8. What information will be collected

From baseline to 3 months, to 6 months, and to 12 months, we will measure change in:

- a. **Frequency of opioid use.** We will assess frequency of opioid use in the past three months from 1 = never to 6 = over 20 times.
- b. **Frequency of alcohol and cannabis use.** We will assess frequency of opioid use in the past three months from 1 = never to 6 = over 20 times.
- c. **Social Network Composition.** Participants will be asked to name 15 contacts (“alters”) who are at least 18 years of age. Participants will rate each of the 15 people on the same set of questions with categorical response options (about demographics, relationship quality, likelihood to use drugs, etc.). For each participant the selected responses will be summed across all the network alters and divided by 15 to produce network composition percentages of the whole set of alters named by the participant (% of AI/ANs, % who engage in heavy drinking).
- d. **Cultural connection.** Cultural connection will be measured with 29 items that address 3 dimensions: identity, traditions, and spirituality. Respondents answer 11 yes/no questions (e.g., I have a traditional person, Elder, or other person who I talk to), and use a scale from 1= “strongly disagree” to 5= “strongly agree” for 18 items (e.g., I feel a strong connection/attachment towards my Native American community or Tribe). We will also measure this via participation in 26 different types of traditional practices (e.g., going to Pow Wows, beading, traditional dancing). Items were based upon extensive research conducted with AIAN young people, parents, and community partners.
- e. **Social Network Structure.** Participants will rate the relationship strength between each of the 15 named alters. For each alter pair they will rate if the two people know each other and, if yes, have they connected recently. Measures of network structure (i.e. network “connectedness”) will be constructed from the set of evaluations for each participant. For example, network “density” will be constructed for the network overall, which is calculated by summing the number of alter pairs who know each other and dividing by the total number of possible ties among 15 alters (105). Individual alter “centrality” will be calculated by summing the number of connections each individual alter has with other alters in the network.

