## 4. Procedures and methods employed for analyzing the data

### Aim 2

*Analysis.* Our analytic approach will focus on use and consequences, cognitions, social networks, and cultural connection outcomes. We will compare opioid education participants to TACUNA+WC participants, with covariates age, gender, and the baseline measure of the outcome of interest. Given the longitudinal design, we may implement more than one analytic method to address this aim. One option is to use a multigroup latent growth model framework using robust maximum likelihood for continuous outcomes or weighted least square mean and variance for categorical outcomes. Alternatively, we may use SAS Proc Mixed will be used for continuous outcomes and SAS Proc Glimmix/NLMixed for categorical outcomes. In addition to examining overall longitudinal trends across the entire study, we will also examine outcomes at each timepoint (3, 6, and 12 month) using multivariable linear regression for normally distributed outcomes and multivariable logistic regression for dichotomous outcomes, controlling for the baseline value of the outcome and participant demographics (age, sex, and sexual and gender diverse identity). The estimated adjusted difference between intervention groups at follow-up (or odds ratio for dichotomous outcomes) and the corresponding 95% confidence interval (CI) will be presented, along with the p-value and Cohen's effect size. Evaluating differences at each timepoint provides estimates of the intervention effect at a given timepoint whereas the longitudinal methods will address patterns of change over the course of the intervention. To enhance interpretability of our results, we will use estimated differences between groups to calculate standardized effect sizes in terms of  $d$  (for continuous variables, using the standard deviation of the opioid education only group as denominator); we will use odds ratio estimates to calculate risk difference and number needed to treat, based on outcome proportions for the opioid education group.

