## 6. Plans for interim and final analysis and statistical analysis of the primary and secondary variables and other data

All analyses detailed above in Section 3 including timepoint specific follow-up as well as overall longitudinal models will compare intervention conditions on change in primary outcomes. Mediation models will include secondary variables (social networks and cultural connectedness) as potential explanatory mechanisms of change.

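### Network composition and density use fixed denominators of 15 and 105, which understate both measures for any participant who names fewer than 15 alters

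*Combined protocol and SAP*

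**What the plan says.** Protocol section 8 defines the network measures. For composition (item c), "Participants will be asked to name 15 contacts" aged 18 or over, then "Participants will rate each of the 15 people on the same set of questions with categorical response options". For each participant, "the selected responses will be summed across all the network alters and divided by 15 to produce network composition percentages". The same sentence describes the product as "network composition percentages of the whole set of alters named by the participant".

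For structure (item e), density is the number of alter pairs who know each other, scaled by "dividing by the total number of possible ties among 15 alters (105").

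No rule is given for a list shorter than 15, or for an alter or pair left unrated. SAP section 3 has one general sentence on missing data (multiple imputation and/or full information maximum likelihood) that does not mention alters.

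The measures are used twice. Under Aim 2, SAP section 4 says "Our analytic approach will focus on use and consequences, cognitions, social networks, and cultural connection outcomes". Under Aim 3, SAP section 6 says "Mediation models will include secondary variables (social networks and cultural connectedness) as potential explanatory mechanisms of change".

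**The concern.** The formula and the description agree only when the list has exactly 15 names. For a shorter list, the formula mixes the size of the list into a quantity meant to describe its make-up: each missing name adds nothing to the numerator but stays in the denominator. The resulting score is complete, so the general missing-data provision has no missing value to act on. An unrated alter or pair would have a similar effect if it were scored as zero, though the protocol does not say how such items are scored.

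What is at stake is the network outcomes in Aim 2 and the network mediators in Aim 3. A shorter list would read as a lower share of heavy-drinking contacts and as a less dense network. TACUNA includes "discussion of how to cultivate healthy social networks and cultural worlds" and social network visualization, and the control workshop is not described as including either. It is therefore possible that list length would differ by arm. If it did, part of an apparent network effect or mediated effect could come from list length alone.

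**Working it through.** **The plan's own figure.** Possible ties among 15 alters = 15 × 14 / 2 = 105. This reproduces the stated denominator, which is right for a list of 15.

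**Exact effect of a short list.** With k alters named and all of them rated:

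- reported composition / composition of the named set = k/15
- reported density / density of the named set = [k(k-1)/2] / 105 = k(k-1)/210

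| k | pairs k(k-1)/2 | composition factor | density factor |
|---|---|---|---|
| 15 | 105 | 100% | 100% |
| 14 | 91 | 93.3% | 86.7% |
| 13 | 78 | 86.7% | 74.3% |
| 12 | 66 | 80.0% | 62.9% |
| 10 | 45 | 66.7% | 42.9% |
| 8 | 28 | 53.3% | 26.7% |

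Example: 10 alters named, 4 of them heavy drinkers. The share of those named is 4/10 = 40%; the stated rule gives 4/15 = 26.7%. A density of 0.50 among the same 10 becomes 0.50 × 45/105 = 0.214. A measure whose true value is zero is unaffected.

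**Equal shortfall in both arms.** If everyone named 12, a true 10-point difference in composition would be reported as 10 × 12/15 = 8 points. No false difference arises. In simulation with 20% of each arm naming only 10, the false-positive rate stayed at about 5%.

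**Unequal shortfall.** This needs inputs that the documents do not give. Number per arm: 370 × 0.8 / 2 = 148, which matches SAP section 4. Assumed: the same true 30% share in both arms, and list lengths drawn with means 14 and 12 and SD 2, then capped at 15. Capping brings the realised means to about 13.6 and 11.9 (13.61 and 11.95, a gap of 1.66).

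- Spurious difference = 0.30 × 1.66 / 15 = 0.033, about 3.3 percentage points.
- The false-positive rate (two-sided 5% t-test, no true difference) depends on the between-person SD of the true share, which is also assumed:

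| between-person SD | divide by 15 | divide by k |
|---|---|---|
| 0.10 | about 53% | about 5% |
| 0.15 | about 39% | about 5% |
| 0.20 | about 29% | about 5% |
| 0.25 | about 24% | about 5% |

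With a smaller gap (14 versus 13 before capping), the rate is about 11% at SD 0.20 and 15% at SD 0.10. These are unadjusted tests at a single visit. The plan's models also adjust for the baseline value of the outcome, so the rates are illustrations and not predictions for this trial.

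**The case against.** The strongest reply is that section 8 describes a fixed-size network throughout: 15 contacts are named, each of the 15 is rated, and ties are rated among the 15. If the survey will not proceed without 15 complete entries, then 15 and 105 are the correct denominators, the description and the formula agree, and there is no bias. This stands as a condition. The documents neither say that 15 names are compulsory nor show that short lists occur. What remains is that being asked for 15 is weaker than being required to give 15, and the written rule yields a wrong percentage for any shorter list that is accepted.

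A reader might infer that the trial's arm comparisons on networks will be biased, or that TACUNA will make participants name fewer people. The documents do not support either. A false difference needs list length or item response to differ by arm after randomisation; one arm's focus on networks makes that possible, not established. Nor do the documents say that unanswered alter questions are counted as a no. That would follow only if they are scored as zero, and imputation at item level is not ruled out.

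It can also be said that a count out of a fixed 15 is a legitimate measure of exposure, since fewer heavy-drinking contacts may be a real gain. That is fair for a count, but the protocol calls this measure a percentage of the alters named, which is a different quantity.

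Finally, SAP section 6 calls these variables secondary. That is right, and it limits the weight of the point: the participants' own opioid, alcohol and cannabis use outcomes are untouched.

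**Conclusion.** The point holds in conditional form. For any participant with k < 15 alters, the stated rule understates nonzero composition by the factor k/15 and nonzero density by k(k-1)/210. That is exact arithmetic and needs no assumption about how often it happens. An equal shortfall in the arms lowers levels and shrinks a true difference in raw units. An unequal shortfall can also create a difference where none exists: about 3.3 points, with about 24% to 53% false positives, under the assumed share, list lengths and SD range of 0.25 to 0.10. The documents show neither short lists nor a difference in length by arm, so those figures show sensitivity and not expected error. The reach is limited to the secondary network outcomes in Aim 2 and the network mediators in Aim 3. There is no effect if every participant names and rates 15. The change is worth making because it is nearly free and leaves results for complete lists unchanged.

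**What to change.** State in Protocol section 8 whether the survey requires 15 fully rated alters. If it does, one sentence saying so closes the point.

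If it does not:

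- Divide composition by the number of alters named with a valid answer to that item.
- Divide density by the number of rated pairs, which is k(k-1)/2 when all pairs among the k named alters are rated.
- Report k by arm and visit, so that any difference in list length can be seen.

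A minimum k should not define the main analysis. Any cut-off would be arbitrary, and it would make outcomes missing according to a variable measured after randomisation. It can serve as a sensitivity analysis.

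The cost is a line or two of wording and code, with no new data. The downside is that percentages from very short lists are noisier. Where all 15 are named and rated, results are identical to those under the present rule.

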# Statistical Analysis Plan (SAP)

*The statistical analysis plan outlines a proposed method to describe and define the following aspects of the study.*

## 1. Statistical aspects of the clinical trial design

**Aim 2.** We will compare outcomes at 3-, 6- and 12-months for AI/AN EAs who receive opioid education (n=185) to AI/AN EAs who receive TACUNA+WC (n=185).

**Aim 3.** We will conduct mediation analyses to examine whether changes in social networks and cultural connectedness serve as explanatory mechanisms for reductions in opioid and AOD use.

**Aim 4. Sustainability.** We will develop and test strategies to facilitate sustainability of TACUNA within these communities through 20 key informant interviews.

**Aim 5. Economic evaluation.** We will follow recommendations from the Panel of Cost-Effectiveness in Health and Medicine, by reporting costs and cost-effectiveness estimates in terms of two reference cases, one based on a program perspective (programmatic and provider time costs) and the other on a societal perspective that incorporates a broader range of costs, such as opportunity costs to participants.

## 2. Process of data selection for analyses

Data will be selected for analysis in order to address study aims focused on evaluating the intervention in terms of primary and secondary outcomes as well as determining mediating mechanisms of change.

## 3. Detailed analyses of data items

*Descriptives.* We will examine descriptive statistics and examine missing data. Frequencies will be evaluated for evidence of sparseness for categorical data and for non-normality (using plots, examination of skewness, kurtosis, etc.) for continuous variables. If sparseness is present for categorical variables, we will collapse as necessary to produce cell sizes sufficient for analysis. Where non-normality is evident, variables may be transformed. Outliers may be recoded or omitted if necessary. Missing data will be dealt with using multiple imputation and/or full information maximum likelihood estimation. All outcomes will be presented using descriptive statistics; continuous variables by the mean and standard deviation (SD), and dichotomous variables by the number and percentage. Descriptive statistics will be provided at both baseline and follow-up.

*Baseline equivalence across experimental groups.* We will evaluate comparability of experimental groups with respect to potential confounders. Categorical methods of analysis (e.g. cross tabulations, chi-square) will be used to compare groups for discrete data (e.g., employment, school status). ANOVA or t-tests will be used to test for homogeneity of groups for continuous data at baseline. If a statistically significant difference is found, the covariates will be included in all subsequent analyses.

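### SAP section 3 lets valid outcome values be omitted under an undefined outlier rule and lets chance baseline differences pick covariates; keep all valid values and fix one covariate list.

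*Combined protocol and SAP*

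**What the plan says.** **Outliers.** SAP section 3 (Descriptives) says "Outliers may be recoded or omitted if necessary". Neither document defines an outlier, gives a cut-off, says who decides or when, or plans a sensitivity analysis. Protocol section 2 (Phase 2/UH3) describes the trial as unmasked. On missing data, SAP section 3 says "Missing data will be dealt with using multiple imputation and/or full information maximum likelihood estimation".

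**Use items.** Protocol section 8 defines the opioid item: "We will assess frequency of opioid use in the past three months from 1 = never to 6 = over 20 times". SAP section 4 (Aim 2) offers "multivariable linear regression for normally distributed outcomes and multivariable logistic regression for dichotomous outcomes" at each timepoint. For the longitudinal analysis it offers separate routes for continuous and for categorical outcomes. It does not say which route the 1–6 items take.

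**Covariates.** SAP section 3 plans chi-square tests, ANOVA or t-tests between arms at baseline. The variables are given only by example: these methods "will be used to compare groups for discrete data (e.g., employment, school status"). Then: "If a statistically significant difference is found, the covariates will be included in all subsequent analyses". No significance level is stated. SAP section 4 already names core covariates, but in two ways. The main comparison is made "with covariates age, gender, and the baseline measure of the outcome of interest". The timepoint regressions use the baseline value and "participant demographics (age, sex, and sexual and gender diverse identity").

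**The concern.** On a bounded 1–6 item every recorded answer is valid. If most participants answer never, the values that look extreme are those of the heaviest users, the people a prevention trial most needs to count. The arm with more users loses more of them, so omission pulls the comparison toward no effect. If the decision to keep, recode or omit is left until outcomes are seen by arm, it is also a free choice among analyses.

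The covariate rule is a separate and lesser matter. With randomised arms, a baseline difference is a chance event, and a between-arm p-value does not show that a variable predicts the outcome. The rule therefore lets chance decide what is added to every later model, starting from a core set that is itself worded in two ways.

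**Working it through.** **1. Inputs.** From SAP section 4 (Power): 148 per arm after 20% attrition, correlation 0.50, four timepoints, alpha .05 (taken as two-sided), d = 0.31. The documents give no user rates, spread of use, number of baseline tests or covariate strengths. Those below are assumptions.

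**2. The plan's own figure reproduces.** 148/0.80 = 185 per arm, 370 in total. For a linear time contrast over four equally spaced visits, SD = 3 × √(0.5/5) = 0.949. Power = Φ(0.31/(0.949 × √(2/148)) − 1.96) = Φ(0.85) = 80.3%. With visits at 0, 3, 6 and 12 months it is 79.6%. The sample size is not in dispute. For a single timepoint adjusted for baseline, SD = √0.75 = 0.866 and power is 86.8%.

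**3. Omission by hand.** Assume 10% v 5% users, spread evenly over categories 2–6, and a cut-off at the pooled mean+3SD.
- Pooled use is 7.5%. Mean = 1 + 0.075 × 3 = 1.225. Variance = 0.075 × 11 − 0.225² = 0.774, so SD = 0.880. Cut-off = 1.225 + 2.640 = 3.86.
- Categories 4–6, three fifths of users, are flagged: 148 × 0.06 = 8.9 controls and 148 × 0.03 = 4.4 TACUNA participants.
- True difference: 0.05 × 3 = 0.150.
- After omission: (0.02×1 + 0.02×2)/0.94 − (0.01×1 + 0.01×2)/0.97 = 0.064 − 0.031 = 0.033.
- In samples where the cut-off falls just above 4, category 4 survives and the difference is 0.125 − 0.061 = 0.064. The average over trials lies between the two.
- Capping at 3.86 instead leaves 0.116.

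**4. Simulation.** 8,000 trials per setting, 148 per arm, ANCOVA on baseline. Users are spread mostly low / evenly / mostly high.

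| Users | Quantity | Keep | Omit | Cap |
|---|---|---|---|---|
| 10% v 5% | difference | 0.114/0.148/0.181 | 0.044/0.048/0.054 | 0.088/0.115/0.146 |
| | power % | 38/40/42 | 27/22/19 | 43/43/43 |
| 20% v 10% | difference | 0.231/0.300/0.361 | 0.156/0.200/0.271 | 0.210/0.281/0.352 |
| | power % | 73/75/76 | 67/65/66 | 76/77/77 |

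Omission removes 61/68/70% of the difference at 10% v 5% (for example 1 − 0.044/0.114 = 61%) and 32/33/25% at 20% v 10%. Capping removes 19–23% and 2–9%.

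**5. Where it stops.** The cut-off passes 6, so nothing is flagged, once pooled use exceeds about 38/23/17%. At 40% v 30% only the mostly-low spread changes (0.234 to 0.224). For a near-normal outcome, omission moves 0.309 to 0.303 and power 85.8% to 85.3%.

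**6. Does likelihood-based handling repair it?** With flagged values set to missing and a three-visit maximum-likelihood model (1,500 trials), the 10% v 5% differences still fall from 0.116/0.147/0.177 to 0.048/0.051/0.055. Values removed because they are high are not missing at random. Multiple imputation under the same assumption would share the problem.

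**7. Free choice of rule, no true effect.** Taking the smallest p of keep, omit and cap rejects 4.7–9.6% over user rates of 5–40%, and about 8–10% when use is rare. Choosing only between keep and cap gives 4.7–6.4%. A log-normal outcome with four rules gave about 5% for each rule alone and 10.6% for the best of four.

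**8. Covariate rule.** The chance that at least one of k independent variables is significant at .05 is 1 − 0.95^k: 10% (k=2), 23% (5), 40% (10), 64% (20). Power at d = 0.31, 20,000 trials per setting, baseline outcome always adjusted:

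| r with outcome, r with baseline | Core | Rule | Always adjust |
|---|---|---|---|
| 0.3, 0.3 | 86.6 | 86.6 | 87.3 |
| 0.5, 0.5 | 86.6 | 86.8 | 89.9 |
| 0.3, 0 | 86.8 | 87.4 | 90.4 |
| 0.5, 0.3 | 86.5 | 87.2 | 92.1 |
| 0.5, 0 (extreme) | 86.6 | 87.9 | 96.3 |

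Rule against always adjusting: 0.7–4.9 points lower in the first four settings, 8.5 in the extreme one. Rule against core: 0.1–1.3 points higher, and up to 1.5 in a rerun. Null rejection under the rule was 4.2–5.0% (3.7–4.8% in the rerun).

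**The case against.** The strongest reply is that the large outlier figures come from an analysis the SAP may never run. At each timepoint, linear regression is kept for normally distributed outcomes. Dichotomous and categorical outcomes have their own methods, sparse categories are to be collapsed, and the economic section treats opioid misuse as abstention. Where linear regression clearly fits, omission is trivial. This stands as a limit on size. It does not remove the point, because the continuous longitudinal route is open to these items and the outlier sentence exempts none.

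A reader might infer that the trial will delete its heavy users. The text does not say so: it permits omission or recoding if needed and names no variable. Nor does omission by itself manufacture a positive result, since the bias shown is toward no effect. The 8–10% figure needs someone to pick the smallest of three p-values.

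On covariates, a reader might infer that baseline testing inflates type I error or damages the pre-stated model. Neither holds: null rejection is at or just below 5%, and the rule slightly beats the core model. The power gain therefore comes only if a truly prognostic variable is named. The two lists in SAP section 4 also need not be a contradiction, since they introduce different analyses; harmonising them is tidying.

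Finally, capping gives equal or higher power than raw values in the rare-use runs, so barring it from the primary analysis would be a preference. That is accepted: what matters is that its cut-off is fixed in advance.

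**Conclusion.** The point holds, and the plan should be changed. The main part is the open permission to omit valid values. Its size depends on a rare-use item being analysed as continuous, and on an assumed mean+3SD cut-off, user rates and spreads. Under those conditions a true difference shrinks by about 60–70% (10% v 5% users) or 25–33% (20% v 10%), and the planned missing-data methods do not restore it. Elsewhere the effect is trivial or absent. Free choice of rule after seeing results could at worst roughly double the 5% error rate.

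The secondary part is that chance shapes the adjustment set. Its cost is an unpredictable model and about 0.7–5 power points relative to always adjusting for a covariate that is in fact prognostic, with correlations assumed. It is not a validity problem. Neither part touches the sample size.

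**What to change.** **Outliers.** Remove the option to omit. Keep all valid values from all randomised participants in the primary analysis, and correct only verified data errors. Any recoding or capping, primary or sensitivity, should use a cut-off written into the SAP before follow-up data are seen by arm, with the uncapped result shown beside it.

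**Covariates.** Delete the baseline significance tests and the inclusion rule, and report baseline characteristics descriptively. Use one fixed list in all Aim 2 models and in the Aim 3 mediation models, for which the SAP names no covariates of their own: baseline value of the outcome, age, sex, and sexual and gender diverse identity (the fuller list in SAP section 4), plus employment and school status, named now.

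**Cost.** SAP wording, with N unchanged at 370. Non-prognostic terms cost about 0.1 power point for one, 0.3 for three and 1.2 for ten (148 per arm, d = 0.31, baseline r = 0.5). If a prognostic variable is left off the list, up to about 1.5 points are lost against the current rule. Keeping extreme valid values leaves skewed outcomes, which need a model or standard errors suited to them.
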